##### 4.2. Exclusion Criteria

Patients are excluded from the study if any of the following criteria apply:

1. Evidence of critical COVID-19 based on:
  - a. Respiratory failure (defined by endotracheal intubation and mechanical ventilation, oxygen delivered by noninvasive positive pressure ventilation, or clinical diagnosis of respiratory failure in setting of resource limitations)
  - b. Septic shock (defined by investigator assessment or requires vasopressor)
  - c. Multiple organ dysfunction/failure
2. In the opinion of the investigator, unlikely to survive for at least 48 hours from screening
3. Inadequate hematologic parameters as indicated by the following labs:
  - a. Patients with severe neutropenia ( $ANC < 1000 \times 10^9/L$ ) or
  - b. Thrombocytopenia (e.g., platelets  $< 100,000$  per microliter of blood)
4. Inadequate renal and liver function as indicated by the following labs:
  - a. Creatinine clearance (CrCL)  $< 20$  mL/min using the formula of Cockcroft and Gault.
  - b. Aspartate transaminase (AST) or alanine transaminase (ALT)  $> 5$  x upper limit of normal (ULN)
5. Hyponatremia defined as sodium  $< 130$  mEq/L
6. Unable to take oral medication when informed consent is obtained.
7. Patients with a legal guardian or who are incarcerated.
8. Treatment with strong CYP3A inhibitors or inducers. A list of strong CYP3A inhibitors and inducers is provided in [Appendix 3](#).
9. Pregnant and breastfeeding women.

#### **4.3. Screen Failures**

Screen failures are defined as patients who consent to participate in the clinical study but are not subsequently randomized for treatment in the study. Minimal information is required for these patients including demographics, screen failure details, eligibility criteria, and any serious adverse event (SAE) not related to COVID-19.

Individuals who do not meet the criteria for participation in this study (screen failure) may be rescreened. Rescreened patients should be assigned the same patient number as for the initial screening.

#### **4.4. Randomization/Stratification**

Randomization will be performed prior to dosing.

Randomization will be stratified based on the following stratification factors and will maintain the 2:1 allocation between treatment arms (selinexor vs placebo) within each of the stratification categories:

- Use of concomitant therapies: an anti-viral (e.g., remdesivir) or an anti-inflammatory (e.g. hydroxychloroquine, biologics targeting e.g., IL-6 or IL-1).

Note: acetaminophen and nonsteroidal anti-inflammatory drugs (NSAIDs) will not constitute anti-inflammatory agents for the purposes of stratification.

- High Risk Comorbidities: Age > 75, BMI > 30, cancer patients on chemotherapy, patients with cardiac (CAD, AMI, CHF) or pulmonary (COPD, emphysema) disease, diabetes, hypertension. Stratification will be based on number of high risk comorbidities: (1 vs  $\geq 2$  vs 0)

## 5. STUDY TREATMENT

### 5.1. Study Treatment Administered

**Table 3: Study Treatment Administered**

|                                |   |
|--------------------------------|---|
| Treatment Name          | Selinexor (XPOVIO ® , KPT-330) / Placebo |
| Type                    | Drug  |
| Dose Formulation        | Tablet  |
| Unit Dose Strength      | 20 mg   |
| Dosage Level            | 20 mg, single dose                                  |
| Route of Administration | Oral  |

A dose of 20 mg selinexor or matching placebo will be administered orally on Days 1, 3, and 5 of each week for up to 2 weeks. If the patient is tolerating therapy and clinically benefitting (defined below), dosing can continue for an additional 2 weeks (on Days 15, 17, 19, 22, 24, and 26).

### 5.2. Dosing and Administration of Selinexor/Placebo

#### 5.2.1. Labeling

Medication labels for each blister pack of selinexor and matching placebo tablets will be in the local language and comply with the legal requirements of each country. They will include storage conditions for the drug and the kit identification number, with a space to record the patient ID number after the IMP is assigned.

#### 5.2.2. Dispensing Directions

The Investigator or responsible site personnel must instruct the patient or caregiver to take the study treatment as per protocol. Study treatment will be dispensed to the patient by authorized site personnel only. Additional dispensing instructions will be provided in the Pharmacy Manual.

#### 5.2.3. Dosing Information

Study treatment tablets should be taken orally with at least 120 mL (4 ounces) of water. Study treatment can be taken with or without food. In order to avoid contact with skin, tablets must be swallowed whole and should not be crushed.

Eligible patients must be able to take oral medication when informed consent is obtained. If a patient is later intubated or unable to take oral medication during treatment, it is permissible to use selinexor suspension prepared as below:

A suspension of selinexor and/or placebo can be prepared by the site pharmacy from selinexor tablets, water, and the commercial suspension agent Ora-Blend®. The pharmacy should place one 20 mg active or placebo tablet in a bottle (amber if available) and add 3 mL of water to disintegrate the tablet, then add 9 mL of Orablend® suspending agent. Gentle swirling or

inversion of the capped bottle will mix the suspension and suspend selinexor for dosing. The resulting suspension should be dosed within 4 hours. Administer the suspension to the patients using an oral dosing syringe via a nasogastric (NG) or percutaneous endoscopic gastrostomy (PEG) feeding tube. Rinse the bottle, syringe and tube with 40 mL to 110 mL of saline and dose the saline rinse to the patient to ensure complete delivery of the selinexor/placebo dose.

Handling Precaution: Selinexor tablets are coated for easy handling. Do not break, cut, or crush selinexor tablets because of increased risk of dermatologic toxicity (e.g., rash) from exposure to the active ingredient in the tablets.

Handling Precaution: The tablets quickly disintegrate in water (<10 min) without being crushed. Please wear gloves when handling the suspension to prevent unintended exposure to the active ingredient. The site pharmacy should consult the pharmacy manual for full instructions on preparing and handling the suspension and for alternative suspending agents should Ora-Blend® be unavailable.

### **5.3. Missed or Vomited Doses of Selinexor**

#### **5.3.1. Missed Doses of Selinexor**

Missed selinexor doses should be managed as follows:

- If a dose was missed, the dose should be taken the next day. Subsequent doses must respect the required 48 hour interval planned schedule. All missed and delayed doses should be documented
- If a dose must be skipped (e.g., due to recommendation of treating physician), the next dose will be taken as per schedule. All missed and delayed doses should be documented.

#### **5.3.2. Vomited Doses of Selinexor**

If a dose is vomited  $\leq 1$  hour after ingestion and an intact tablet is seen, it will be replaced. If vomiting occurs more than 1 hour after dosing, it will be considered a complete dose.

### **5.4. Preparation/Handling/Storage/Accountability**

- The Investigator or designee must confirm appropriate temperature conditions have been maintained during transit for all study treatment received and any discrepancies are reported and resolved before use of the study treatment.
- Only patients randomized in the study may receive study treatment and only authorized site staff may supply or administer study treatment. All study treatment must be stored in a secure, environmentally controlled, and monitored (manual or automated) area in accordance with the labeled storage conditions with access limited to the Investigator and authorized site staff.
- The Investigator, institution, or the head of the medical institution (where applicable) is responsible for study treatment accountability, reconciliation, and record maintenance (i.e., receipt, reconciliation, and final disposition records).

- Further guidance and information for the final disposition of unused study treatment are provided in the Pharmacy Manual.

## 5.5. Study Treatment Compliance

Administration of study treatment will be documented at each timepoint specified in the SoA. Deviation(s) from the prescribed dosage regimen should be recorded in the eCRF.

## 5.6. Concomitant Medication

### 5.6.1. Recommended Concomitant Treatments

Provide prophylactic concomitant treatment with a 5-HT3 antagonist and/or other anti-emetic agents prior to and during treatment with selinexor.

Ensure that patients are maintaining adequate fluid status and administer intravenous hydration as clinically warranted during the study treatment.

### 5.6.2. Prohibited/Permitted Concomitant Medications

If in the physician's judgement, it is in the best interest of the patient to use anti-viral or anti-inflammatory treatments, these treatments are to be documented in the patient's chart and entered in the electronic case report form. Use of these treatments should be carefully considered as they could potentially confound data interpretation.

The use of strong CYP3A inhibitors or inducers while on selinexor treatment is not permitted. Selinexor should be interrupted during the use of these agents. See [Appendix 3](#) for a list of strong CYP3A inhibitors and inducers.

## 5.7. Dose Modifications

Each dose modification or treatment delay must be documented, including the respective reason. The reason for dose modification should be directly related to a selinexor-associated AE, and not due to disease symptom/sign or to other medications.

For all Grade  $\geq 3$  hematological or non-hematological AEs that are NOT selinexor related, after consultation with the Medical Monitor and at the discretion of the Investigator, selinexor dosing may be maintained.

Selinexor should be discontinued for all selinexor-related life-threatening (Grade 4) AEs.

[Table 4](#) summarizes the selinexor dose levels; [Table 5](#) describes supportive care and dose adjustment guidelines. Deviations from the guidelines are permitted after discussion between the Sponsor and the treating physician.

**Table 4: Selinexor Dose Modification Steps for Adverse Reactions**

| Recommended Starting Dosage                                     | First Reduction  |
|---|--|
| 20 mg
Days 1, 3 and 5 of each week
(60 mg total per week) | 20 mg
Days 1 and 3 weekly
(40 mg total per week) |

**Table 5: Selinexor Dosage Modification for Adverse Reactions**

| Adverse Reaction a  | Occurrence | Action   |
|--|------------|--|
| Hematologic Adverse Reactions   |            |  |
| Thrombocytopenia  |            |  |
| Platelet count 25,000 to less than 50,000/mcL                                    | Any        | 
 
• Reduce selinexor by 1 dose level (see Table 4).
 
  |
| Platelet count 25,000 to less than 50,000/mcL with concurrent G3 bleeding | Any        | 
 
• Interrupt selinexor and provide appropriate supportive care.
 
• Restart selinexor after bleeding has resolved at 1 dose level lower (see Table 4).
 
   |
| Platelet count less than 25,000/mcL  | Any        | 
 
• Interrupt selinexor and provide appropriate supportive care.
 
• Monitor until platelet count returns to at least 50,000/mcL.
 
• Restart selinexor at 1 dose level lower (see Table 4).
 
   |
| Neutropenia   |            |  |
| Absolute neutrophil count of 0.5 to 1.0 x 10  /L with fever   | Any        | 
 
• Interrupt selinexor and provide appropriate supportive care.
 
• Monitor until neutrophil counts return to 1.0 x 10^9/L or higher.
 
• Restart selinexor at 1 dose level lower (see Table 4).
 
  |
| Absolute neutrophil count less than 0.5 x 10  /L                     | Any        | 
 
• Interrupt selinexor and provide appropriate supportive care.
 
• Monitor until neutrophil counts return to 1.0 x 10^9/L or higher.
 
• Restart selinexor at 1 dose level lower (see Table 4).
 
  |
| Anemia  |            |  |
| Hemoglobin less than 8.0 g/dL  | Any        | 
 
• Reduce selinexor by 1 dose level (see Table 4).
 
• Administer blood transfusions and/or other treatments per clinical guidelines.
 
  |
| Life-threatening consequences  | Any        | 
 
• Interrupt selinexor and administer appropriate care with blood transfusions and/or other treatments per clinical guidelines.
 
• Monitor until patient stabilizes and hemoglobin is >8.0 g/dL.
 
• Restart selinexor at 1 dose level lower (see Table 4).
 
 |
| Non-Hematologic Adverse Reactions   |            |  |
| Hyponatremia  |            |  |
| Sodium level 130 mmol/L or less not due to disease or fluid status               | Any        | 
 
• Interrupt selinexor and provide appropriate supportive care.
 
• Monitor until sodium levels return to 130 mmol/L or higher.
 
  |

| Adverse Reaction a   | Occurrence                     | Action   |
|---|--------------------------------|--|
| 
 
Restart selinexor at 1 dose level lower (see Table 4).
 
  |                                |  |
| Nausea and Vomiting  |                                |  |
| Grade 1 or 2 nausea (oral intake decreased without significant weight loss, dehydration or malnutrition)
OR Grade 1 or 2 vomiting (5 or fewer episodes per day) | Any                            | 
 
Maintain selinexor and initiate additional anti-nausea medications.
 
  |
| Grade 3 nausea (inadequate oral caloric or fluid intake)
OR Grade 3 or higher vomiting (6 or more episodes per day)   | Any                            | 
 
Interrupt selinexor.
 
Monitor until nausea or vomiting has resolved to Grade 2 or lower or baseline.
 
Initiate additional anti-nausea medications for Grade 2 or lower.
 
Restart selinexor at 1 dose level lower (see Table 4)
 
 |
| Diarrhea   |                                |  |
| Grade 2 (increase of 4 to 6 stools per day over baseline)   | 1 st                | 
 
Maintain selinexor and institute supportive care.
 
  |
|   | 2 nd and subsequent | 
 
Reduce selinexor by 1 dose level (see Table 4).
 
Institute supportive care.
 
  |
| Grade 3 or higher (increase of 7 stools or more per day over baseline; hospitalization indicated)   | Any                            | 
 
Interrupt selinexor and institute supportive care.
 
Monitor until diarrhea resolves to Grade 2 or lower.
 
Restart selinexor at 1 dose level lower (see Table 4).
 
   |
| Weight Loss and Anorexia   |                                |  |
| Weight loss of 10% to less than 20%
OR anorexia associated with significant weight loss or malnutrition not due to intensive care status                        | Any                            | 
 
Interrupt selinexor and institute supportive care.
 
Monitor until weight returns to more than 90% of baseline weight.
 
Restart selinexor at 1 dose level lower (see Table 4).
 
  |
| Other Adverse Reactions  |                                |  |
| Grade 3 or 4 non-hematologic reactions  | Any                            | 
 
Interrupt selinexor.
 
Monitor until resolved to Grade 2 or lower, restart selinexor at 1 dose level lower (see Table 4).
 
   |
| Life-threatening hematological and non-hematological (Grade 4) AEs related to selinexor  | Any                            | 
 
Discontinue selinexor
 
  |

a National Cancer Institute Common Terminology Criteria for Adverse Events (NCI CTCAE) version 5.0. Only adverse reactions to selinexor should lead to dose adjustments.

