### **6.2. Patient Discontinuation/Withdrawal from the Study**

A patient may withdraw from the study at any time at his/her own request or may be withdrawn at any time at the discretion of the Investigator for safety, behavioral, compliance, or administrative reasons. Waivers for eligibility criteria for enrollment will not be permitted. The criteria given below are reasons the investigator must consider for removal of patients from study.

The Investigator must determine the primary reason for a patient's discontinuation of study treatment/withdrawal from the study and record this information on the electronic case report form (eCRF).

The Investigator may remove a patient from study treatment for any of the following reasons:

- Unacceptable AEs or toxicity that cannot be managed by supportive care
- Significant deviations from inclusion/exclusion criteria
- Missed / unscheduled / off-schedule / incomplete / incorrect assessments that result in patients being put at risk
- Any other medically appropriate reason or significant protocol violation, in the opinion of the Investigator.

The Investigator must remove a patient from study treatment for any of the following reasons:

- Patient withdraws consent to continue study treatment.
- Worsening clinical condition defined as at least 5 days of intubation/ECMO with no evidence of clinical improvement. Patients who are clinically stable based on oxygen requirements on mechanical ventilation will be permitted to remain on study.
- Grade  $\geq 3$  nausea or vomiting despite optimal antiemetic therapy.
- Progression of renal dysfunction requiring dialysis.
- Grade 4 AEs related to selinexor.

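### Four Table 5 rows restart selinexor after reactions that can be Grade 4 or life-threatening, Section 6.2 and the synopsis require stopping, and no text says which rule governs

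*Protocol*

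**What the plan says.** **Restart rows (Protocol Table 5).** Each row below tells the site to interrupt selinexor, wait for recovery and restart one dose level lower:

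- anemia with life-threatening consequences: "Interrupt selinexor and administer appropriate care with blood transfusions and/or other treatments per clinical guidelines", with restart once the patient is stable and hemoglobin is above 8.0 g/dL;
- "Grade 3 or higher vomiting (6 or more episodes per day");
- diarrhea: "Grade 3 or higher (increase of 7 stools or more per day over baseline; hospitalization indicated");
- "Grade 3 or 4 non-hematologic reactions".

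Footnote a limits the whole table to drug reactions: "Only adverse reactions to selinexor should lead to dose adjustments".

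**Stop rules.** The last row of Table 5 orders discontinuation for "Life-threatening hematological and non-hematological (Grade 4) AEs" related to selinexor. Section 5.7 says, and Section 6.1 repeats: "Selinexor should be discontinued for all selinexor-related life-threatening (Grade 4) AEs". Section 6.2 lists "Grade 4 AEs related to selinexor" among the reasons for which the investigator must take the patient off study treatment. The synopsis has the same item in its list of events that stop therapy before Day 28.

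**Between the two.** Section 5.7 describes Table 5 as guidelines and allows departures from them after discussion with the sponsor. No sentence ranks the restart rows against the stop rules.

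**The concern.** A dose-modification table is used at the bedside, and staff will usually look up the row that names the event. For a life-threatening anemia attributed to selinexor, one row of Table 5 orders an eventual restart and another orders discontinuation. For Grade 4 vomiting, diarrhea or other non-hematologic reactions, Table 5 orders a restart and Section 6.2 orders removal from treatment.

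What is at stake is patient safety. A patient who has had a Grade 4 or life-threatening drug reaction could be given the drug again by a site that believes it is complying. That site could then be found in breach of Section 6.2 for having followed Section 5.7.

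**Working it through.** No plan figure needs reproducing here. The check compares triggers and actions row by row, followed by short arithmetic on exposure and frequency.

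**1. Does relatedness reconcile the rules?** No. Footnote a confines every Table 5 row to reactions to selinexor, and the stop rules also concern selinexor-related events. Both sets address the same patients.

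**2. Which rows conflict with which rules?** Sections 5.7 and 6.1 and the last row of Table 5 speak of life-threatening (Grade 4) events. Section 6.2 and the synopsis say Grade 4 without qualification.

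| Table 5 restart row | How it reaches Grade 4 | Against 6.2 and synopsis | Against 5.7, 6.1 and last row |
|---|---|---|---|
| Anemia | Says life-threatening, which the protocol equates with Grade 4 | Conflict | Conflict |
| Other non-hematologic | Names Grade 4 | Conflict | Conflict for AEs without a CTCAE scale |
| Vomiting | Grade 3 or higher | Conflict | Not settled by the documents |
| Diarrhea | Grade 3 or higher | Conflict | Not settled by the documents |

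The entry for AEs without a CTCAE scale rests on Protocol Section 8.1.2.2, which defines Grade 4 for such events as life-threatening. SAP Section 8.1 uses the same mapping. For events with a scale, the documents do not reproduce the CTCAE definitions, so they do not show whether every Grade 4 event is life-threatening.

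**3. How much of the table is affected?** Ten rows end in restart: platelets 25,000 to under 50,000 with Grade 3 bleeding; platelets under 25,000; ANC 0.5 to 1.0 with fever; ANC under 0.5; life-threatening anemia; sodium; nausea/vomiting; diarrhea; weight loss/anorexia; other non-hematologic. Four of the 10 name Grade 4, an open upper grade or a life-threatening event.

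**4. What does one level lower mean?** Table 4 gives a single reduction, from 20 mg on three days a week to 20 mg on two.

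- Weekly dose: (60 − 40) / 60 = 33% less.
- Per dose: 20 mg against 20 mg, 0% less.

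On the reduced schedule, doses to Day 14 fall on Days 1, 3, 8 and 10. As an illustration, after an event following the Day 1 dose:

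- recovered by Day 3: Days 3, 8 and 10 remain, 3 × 20 = 60 mg;
- recovered by Day 8: Days 8 and 10 remain, 2 × 20 = 40 mg;
- recovered by Day 10: 1 × 20 = 20 mg;
- later: 0 mg.

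The count stops at Day 14 because extension criteria 1a and 2e in the synopsis bar patients with a related Grade 4 event. This reads criterion 1 as requiring 1a together with either 1b or 1c.

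**5. How often?** Protocol Table 7 (25 cancer patients on low-dose selinexor, onset by Day 14) shows no Grade 4 vomiting, diarrhea or anemia. For 0 of 25, the exact two-sided 95% upper limit is 1 − 0.025^(1/25) = 13.7% for each term. The table lists only terms seen in at least 3 patients, so it says nothing about rarer reactions. The documents give no rate in COVID-19.

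**The case against.** The strongest reply is that the wording already ranks the rules. Table 5 is a set of guidelines from which departure is allowed, whereas Section 6.2 says must, Sections 5.7 and 6.1 say all, and the last row of Table 5 is a catch-all. The extension criteria point the same way. This stands as evidence of intent: discontinuation is very probably what was meant. It is still an inference, and a row specific to an event can as plausibly be read as governing that event. Permission to depart from a guideline does not say which of two guidelines is the default.

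The second reply is that other controls would catch the case:

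- Section 7 asks for immediate sponsor discussion of safety concerns, including whether to continue treatment.
- Life-threatening events are SAEs, reportable within 24 hours (Section 8.2.1.3).
- The DSMB reviews interruptions and discontinuations (Section 10.5).
- For vomiting, Section 6.2 also requires stopping when Grade 3 or worse nausea or vomiting persists under optimal antiemetics, and antiemetic prophylaxis is directed for all patients unless contraindicated. The vomiting restart path is therefore narrower than its row suggests.

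These points stand as mitigation. They make an unnoticed restart less likely but leave the conflicting orders in place.

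A reader might infer that the platelet, ANC and sodium restart rows conflict too, because they have no lower limit. The documents do not support counting them, since they do not give the CTCAE cut-offs that would place those values at Grade 4. The single Grade 4 thrombocytopenia in Table 7 does not help without the cut-off. A reader might also cite Section 8.1.2.1 to separate Grade 4 from life-threatening. That section concerns laboratory abnormalities and whether they are serious, so it does not settle the question.

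**Conclusion.** The protocol is inconsistent as written. Four Table 5 rows order restart where Section 6.2 and the synopsis order stopping. The anemia row, and the other non-hematologic row for AEs without a CTCAE scale, also contradict Sections 5.7 and 6.1 and the table's last row. It would go too far to say that all four rows contradict all five stop rules, or that sites have no indication of what was intended.

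The practical size is small: 4 of 10 restart rows, few patients expected, and at most three further 20 mg doses by Day 14 in the illustration above. Efficacy is not affected. Because the possible harm is serious and the correction is cheap, it should be made at the next amendment. The conclusion rests on document wording alone, and on reading footnote a as covering every row. The low expected frequency rests on 25 cancer patients.

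**What to change.** In Table 5:

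1. Cap the vomiting trigger at Grade 3.
2. Cap the diarrhea trigger at Grade 3.
3. Cap the other non-hematologic row at Grade 3.
4. For anemia with life-threatening consequences, replace interruption and restart with discontinuation.
5. Add one line: *Discontinuation for selinexor-related Grade 4 AEs (Sections 5.7, 6.1, 6.2) takes precedence over any restart instruction in this table.*

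The line in item 5 covers the platelet, ANC and sodium rows by default. If the medical monitor wants laboratory values without clinical consequences exempted, the same exemption should appear in Table 5, Section 6.2 and the synopsis stop list, with sodium addressed as well as the blood counts.

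The cost is a wording amendment: four rows and one line, plus a matching phrase in Section 6.2 and the synopsis if an exemption is chosen. It needs IRB/IEC approval (Section 10.1.1) across about 40 planned sites. It adds no procedure, visit or analysis.

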**Exclusion Criteria:**

1. Evidence of critical COVID-19 based on:
  - a. Respiratory failure (defined by endotracheal intubation and mechanical ventilation, oxygen delivered by noninvasive positive pressure ventilation, or clinical diagnosis of respiratory failure in setting of resource limitations)
  - b. Septic shock (defined by investigator assessment or requires vasopressors)
  - c. Multiple organ dysfunction/failure
2. In the opinion of the investigator, unlikely to survive for at least 48 hours from screening.
3. Inadequate hematologic parameters as indicated by the following labs:
  - a. Patients with severe neutropenia (ANC <1000 x 10^9/L) or
  - b. Thrombocytopenia (e.g., platelets <100,000 per microliter of blood)
4. Inadequate renal and liver function as indicated by the following labs:
  - a. Creatinine clearance (CrCL) <20 mL/min using the formula of Cockcroft and Gault.
  - b. Aspartate transaminase (AST) or alanine transaminase (ALT) > 5 x upper limit of normal
5. Hyponatremia defined as sodium less than 130 mEq/L
6. Unable to take oral medication when informed consent is obtained.
7. Patients with a legal guardian or who are incarcerated.

8. Patients taking strong CYP3A inhibitors or inducers. A list of prohibited strong CYP3A inhibitors and inducers is provided in [Appendix 3](#).
9. Pregnant and breastfeeding women.

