**Duration of Treatment and Follow-up:**

Patients will receive study treatment for up to 14 days.

Dosing can continue for an additional 2 weeks if ANY of the following criteria are met:

1. Patients who remain hospitalized must meet the following criteria to continue selinexor therapy:
  - a. has not had a selinexor-related Grade 4 Adverse Event (AE) or selinexor-related Serious AE (SAE) AND
  - b. has not had >1 point ordinal score reduction (worsening) OR
  - c. has 2 point reduction (worsening) in ordinal score with a  $\geq 20\%$  absolute reduction in FiO2 from peak oxygen requirement
2. Patients discharged from the hospital before Day 28 must meet the following criteria to continue selinexor therapy:
  - a. Platelet count > 75,000/mm^3 and
  - b. Neutrophil count >1,000/mm^3 and
  - c. Serum sodium > 130 mmol/L and
  - d. No Grade  $\geq 3$  nausea or vomiting and
  - e. No Grade 4 AEs related to selinexor, and
  - f. Improved ordinal score from baseline AND
  - g. Positive SARS-CoV2 by FDA approved laboratory test at discharge

Note: patients discharged from the hospital who remain on selinexor must continue to have twice weekly serum chemistry and complete blood counts as long as treatment is continued.

Therapy will be stopped if any of the events defined below occur prior to 28 days:

- Patient withdraws consent to continue study treatment.
- Worsening clinical condition defined as at least 5 days of intubation/ECMO with no evidence of clinical improvement. Patients who are clinically stable based on oxygen requirements on mechanical ventilation will be permitted to remain on study.
- Grade  $\geq 3$  nausea or vomiting despite optimal antiemetic therapy.
- Progression of renal dysfunction requiring dialysis.
- Grade 4 AEs related to selinexor

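### Table 5 lets selinexor restart at a sodium of exactly 130 mmol/L, a value that still meets its own interruption trigger when the low sodium is attributed to selinexor

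*Protocol*

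**What the plan says.** Protocol Section 5.7, Table 5, hyponatremia row. The trigger, at any occurrence, is "Sodium level 130 mmol/L or less not due to disease or fluid status". The actions are to interrupt with supportive care, then "Monitor until sodium levels return to 130 mmol/L or higher", then restart one dose level lower. Table 4 gives that level as 20 mg on Days 1 and 3 weekly (40 mg per week). The Table 5 footnote limits the scope: "Only adverse reactions to selinexor should lead to dose adjustments".

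Two other sodium limits appear in the Protocol. Patients discharged before Day 28 may continue treatment only with "Serum sodium > 130 mmol/L and" the other listed conditions (Synopsis, Duration of Treatment and Follow-up; Section 3.1 has the same limit). The entry exclusion is "Hyponatremia defined as sodium less than 130 mEq/L" (Synopsis; same limit in Section 4.2).

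The febrile-neutropenia row of Table 5 interrupts at an absolute neutrophil count of 0.5 to 1.0 × 10⁹/L with fever and sets recovery at 1.0 × 10⁹/L or higher.

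**The concern.** A hold rule and its release rule should not both be true at the same reading. Here they are, at 130 mmol/L. A site with a held patient who recovers to exactly 130 can restart under the recovery bound. If the value is then unchanged and still attributed to selinexor, the same site is back inside a trigger that applies at any occurrence. A patient first measured at exactly 130 meets the trigger and the recovery condition on one result.

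This is a safety threshold for re-dosing, and the row is likely to be used: Protocol Table 7 lists hyponatraemia in 6 of 25 low-dose patients (24%), one of them Grade 3. That says nothing about how often a reading is exactly 130. What is at stake is whether sites dose alike at that value, and how holds and reductions are then counted in SAP Sections 6.7.1 and 8.1.

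**Working it through.** **Boundary check.** Inputs are the two bounds in the hyponatremia row, for sodium attributed to selinexor.

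- Interrupt if Na ≤ 130.
- Release the hold if Na ≥ 130.
- Values meeting both: {Na ≤ 130} ∩ {Na ≥ 130} = {130}.

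At 129 only the interruption applies, at 131 only the release, and at 130 both.

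**After the change.** With release at Na > 130, {Na ≤ 130} ∩ {Na > 130} is empty. The new bound equals the post-discharge limit.

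**Neutrophil row.** Interrupt if 0.5 ≤ ANC ≤ 1.0 and fever; release if ANC ≥ 1.0. These share ANC = 1.0, but only in a patient with fever at that count.

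**Delay the change could cause.** Serum chemistry is scheduled on Days 1, 3, 5, 8, 12, 15, 19, 22 and 26 (Schedule of Assessments, Table 1). The gaps are 2, 2, 3, 4, 3, 4, 3 and 4 days. Dose days at the reduced level are Days 1 and 3 of each week: 1, 3, 8, 10, 15, 17, 22 and 24. Take a held patient with sodium exactly 130 at one check and above 130 at the next. Day 1 is left out because no hold can precede the first dose; days from 15 on apply only to patients who continue past two weeks.

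| Check at exactly 130 | Next check | Wait (days) | Reduced-level doses deferred |
|---|---|---|---|
| Day 3 | Day 5 | 2 | 1 (Day 3) |
| Day 5 | Day 8 | 3 | 0 |
| Day 8 | Day 12 | 4 | 2 (Days 8, 10) |
| Day 12 | Day 15 | 3 | 0 |
| Day 15 | Day 19 | 4 | 2 (Days 15, 17) |
| Day 19 | Day 22 | 3 | 0 |
| Day 22 | Day 26 | 4 | 2 (Days 22, 24) |
| Day 26 | none | – | 0 |

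The largest values are 4 days and 2 doses. They are not hard limits. With the ±1 day windows, the Day 8 check could fall on Day 7 and the Day 12 check on Day 13, a gap of 13 − 7 = 6 days. If sodium is still 130 at Day 12, the hold that could have ended on Day 8 runs to Day 15 at the earliest, 15 − 8 = 7 days. Extra checks, which Section 7.3.4 allows when clinically indicated, shorten all of these.

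**The case against.** The strongest reply is that the row is a sequence: interrupt, wait for recovery, restart lower. The trigger speaks to a patient on drug and the recovery bound to a patient on hold, so a held patient at 130 restarts. A new hold would need fresh attribution to selinexor. Section 7.3.4 has results reviewed before dosing, and Section 5.7 allows departures from the table after discussion with the sponsor. This stands in part. It settles the next step for a held patient, but not what follows when the reading stays at 130 after restart, since the trigger is a level and applies at any occurrence. Nor does it help a patient first measured at exactly 130.

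Several stronger readings are tempting and are not supported.

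- *Every patient at 130 meets both rules.* No: low sodium due to disease or fluid status is outside the trigger.
- *Sodium is the one faulty row.* The weight row does separate its bounds ("Weight loss of 10% to less than 20" percent to interrupt, "Monitor until weight returns to more than 90% of baseline weight" to restart), and the platelet row interrupts below 25,000/mcL and then says "Monitor until platelet count returns to at least 50,000/mcL". The febrile-neutropenia row, however, shares its boundary too.
- *The Protocol contradicts itself on 130 across sections.* Entry, in-hospital dosing and outpatient continuation serve different purposes, and a stricter outpatient limit is not an inconsistency.
- *A patient restarted at 130 has nowhere to go because Table 4 has a single reduction step.* That is a separate matter of detail, which sponsor discussion (Section 5.7) and the investigator's discretion to stop treatment (Section 6.2) can handle.

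**Conclusion.** The point holds as a minor error of wording in a safety threshold. For hyponatremia attributed to selinexor, the interruption and recovery bounds both include 130 mmol/L, and a patient restarted at an unchanged 130 is inside the trigger again. Neither the Protocol nor the SAP says which rule prevails.

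The size is one value on the sodium scale. The documents give no sodium distribution, so no frequency can be estimated. The effect is confined to dosing consistency and descriptive dose-modification counts; the primary analysis, type I error, power and sample size are untouched. The conclusion rests on reading the bounds literally, and on the low sodium still being judged selinexor-related at the time of restart.

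**What to change.** In Table 5, change the sodium recovery bound to above 130 mmol/L. In the same edit, review the febrile-neutropenia row and either separate its bounds at 1.0 × 10⁹/L or state that recovery also requires resolution of fever.

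The alternative for sodium, interrupting only below 130 and leaving recovery at 130 or higher, also removes the overlap and would match the entry criterion. It would allow dosing at 130 and leave the post-discharge rule stricter than the in-hospital one. The sponsor's clinical team should confirm the bound.

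The cost is one threshold edit, a decision on the neutrophil row and a notice to sites, with no added visits, tests or patients. For a patient at exactly 130 there may be a short delay in re-dosing, of the size and under the conditions worked out above.
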